patients.²⁶ In the perioperative population with depressive symptoms, the remission rate was reported to be 23.1% in the ketamine group and 9.3% in the placebo group based on the PASSION study at our research site. We assumed that the remission rate in the esketamine group will be 19.3% and that in the placebo group will be 10%. A sample size of 506 participants will provide 80% power to show the difference between the esketamine group and the placebo group (with a ratio of 1:1), including 1 interim analysis by using a 2-sided significance level of 0.05.²⁷ With the consideration of a 10% attrition rate, the total sample size is planned to be 564.

Interim analysis

The planned interim analysis will be performed after 424 patients (75% of the total sample size) completed the follow-up. This interim analysis will be based on the ITT principle, and the P value will be set at 0.019 following adjustment by O'Brien-Fleming methods.²⁸

Statistical analysis

Continuous variables will be reported as the mean (standard deviation) for normally distributed data and the median (interquartile ranges) for skewed distributions. Categorical variables will be reported as the number (proportion), and the relative risk with its 95% confidence intervals will be calculated. The difference between groups will be reported with 95% confidence intervals of absolute differences calculated by independent t-tests for continuous variables and using the Hodges–Lehmann method for skewed variables. The primary endpoint of remission rate at 3 days after surgery will be analyzed by using the chi-square test or Fisher's exact test. The secondary outcomes will be analyzed using t-tests, Mann–Whitney U tests, and chi-square or Fisher's exact tests as appropriate. The adjusted odds ratios will be estimated by using a logistic regression model by taking into account the unbalanced baseline variables, age, sex, the severity of depressive symptoms, and pain severity after surgery.

For missing values, both imputations with the mean or median or the last observed assessment and multiple imputations will be applied. Sensitivity analysis for different imputation plans will be used to explore the statistical nature of the missing data. All statistical tests will be 2-sided at a significance level of 0.05 and the effect sizes will

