of 10 or greater for the initial diagnosis of depressive symptoms and a MADRS score of 22 or greater for the assessment of severity, with ages ranging from 18--65 years. Major surgeries, including neurosurgical tumor resection, coronary artery bypass grafting, total hip or knee arthroplasty, breast cancer surgery, pneumonectomy or hepatectomy, are estimated to exceed 2 hours. Participants who meet the exclusion criteria will be excluded. Patients who signed the informed consent will be randomized into the esketamine group or the placebo group. In the esketamine group, esketamine will begin to be administered intravenously at a total dose of 0.2 mg/kg per weight and will continue for 40 min. In the placebo group, the same volume of normal saline will be administered at the same infusion rate. All patients will be followed during the perioperative period for depressive symptoms and drug-related complications. The participants will be randomly assigned to the esketamine group or placebo group at a 1:1 ratio. Randomization results will be achieved via a real-time, online system before surgery. A randomized four-block design stratified patients by depressive severity (severe depressive symptoms are defined by MADRS scores equal to or greater than 30). The randomization sequence was created by independent engineers who will keep the allocation blinded, and all study-related investigators will be blinded to the randomization results. Randomization will be performed after informed written consent has been obtained.

Validation of endpoints

The data will be validated according to the prescribed rules. A research manager at each center will determine that all the data are complete, consistent and up-to-date. The research managers are also responsible for retrieving original data and checking and tracking the key endpoint data at the specified time.

Planned analyses

The detailed procedure of analysis in this SAP will be performed only after the database is frozen. The intent-to-treat and per-protocol populations will be determined before unblinding the treatment allocation.

Treatment comparisons

The comparison of interest in this trial is between esketamine and placebo administered intraoperatively over the 3-day period of depressive symptom remission after surgery.

4. Statistical hypotheses

The primary endpoint of this study is the remission rate 3 days after surgery in patients with moderate-to-severe depressive symptoms.

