The intent-to-treat (ITT) population will include all the subjects after randomization and who received esketamine or placebo during surgery. After randomization, it is assumed that all participants have been administered a placebo or esketamine. The modified intent-to-treat population will be excluded from the analysis after randomization situations no longer meet the eligibility criteria, patients who do not have surgery, or patients who cannot undergo follow-up due to surgery-related complications, such as aphasia or coma. The modified ITT population will be tested for demographic characteristics and efficacy and safety outcomes. The population will be used for primary analysis of the efficacy and safety outcomes.

Per-Protocol population

The per protocol (PP) population will comprise all participants except subjects who are confirmed as protocol transgressors. The subjects excluded from the PP population will be confirmed before being blind. This population was used for sensitivity analysis to determine the effect of missing data. In the PP population, subjects will be analysed according to the treatment received and the real events after postoperative assessments.

8. Statistical considerations

The data will be analyzed by Stata 16.0 software (Stata Corp LP, College Station, TX,

USA) and all significance tests will be two-sided, with an alpha setting of 0.05 and 95% confidence intervals confirmed.

Subgroup analysis

The rate of postoperative 3-day remission will be presented at each level of the variables listed below. The degree of change in the treatment effect of each subgroup at different levels will be evaluated via an interaction test.

Multiplicity

The single primary outcome was defined in the protocol, and all other efficacy variables were treated as secondary or other. The only comparison of interest in this study was between esketamine and placebo, and there was no need to adjust for multiple comparisons. All estimates of treatment effects for secondary endpoints will be presented with 95% confidence intervals, no inferential tests will be performed, and only exploratory tests with simple descriptions of these endpoints will be performed.

Missing Data

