The remission rate of depressive symptoms at 3 days postoperative will be summarized by treatment group via the chi-square test or Fisher's exact test to compare the differences between groups in the m-ITT population. The risk ratio for the intervention comparison is presented, and the 95% CI is reported. The results are

also displayed graphically on a histogram plot.

Secondary efficacy analysis

All secondary endpoints are based on the m-ITT population. For categorical variables, which are presented as frequency counts and percentages, a two-sided Pearson's χ^2 test or Fisher's exact test will be used, as appropriate. The odds ratios and 95% CIs were calculated. For continuous variables, prior to performing the statistical analysis, the assumptions of normality and homogeneity of variance of the residuals of quantitative variables were tested via the Shapiro-Wilk test and Levene's test, respectively. For efficacy analysis, a t test (normal variables) or the Mann-Whitney U test (skewed variables) will be used, as appropriate. The absolute difference and 95% CIs were calculated via the Mann-Whitney U test and the Hodges-Lehmann method.

Safety analysis

Safety endpoints will be assessed in the total population. The related variables are presented as frequency counts and percentages in both the esketamine group and the control group, odds ratios and 95% CIs.

Interaction with subgroups

A summary forest plot will be presented on the basis of the predefined subgroups, and interactions between them will be investigated for the primary endpoint. Exploratory subgroup-specific summary statistics and p values for interactions are presented. A separated logistic model was applied for interaction to identify its effect significance. The subgroup analysis included the following covariates: unbalanced baseline variables, age, sex, severity of depressive symptoms and pain severity after surgery.

Main results with Tables

Table 1. Demographic and preoperative characteristics of the total population.

Characteristics	Esketamine group	Control group
Sex		
Female	n (%)	n (%)
Male	n (%)	n (%)
Age, yr,	Mean (SD)/median (IQR)	Mean (SD)/median (IQR)
Height, cm,	Mean (SD)/median (IQR)	Mean (SD)/median (IQR)
Weight, kg,	Mean (SD)/median (IQR)	Mean (SD)/median (IQR)
Education	n (%)	n (%)
Married	n (%)	n (%)
Living state (alone)	n (%)	n (%)
Employed	n (%)	n (%)
Currently smoke	n (%)	n (%)
Alcohol intake		
Never	n (%)	n (%)
Occasional	n (%)	n (%)

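### Part of the adjusted model, and of a forest plot described as predefined, is left to chance baseline imbalances with no rule for identifying them

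*SAP*

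**What the plan says.** **Adjusted model.** After the primary test, the Protocol (Statistical analysis) plans adjusted odds ratios from a logistic model "taking into account the unbalanced baseline variables, age, sex, the severity of depressive symptoms, and pain severity after surgery".

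**Subgroups.** SAP section 8 (Subgroup analysis) states: "The rate of postoperative 3-day remission will be presented at each level of the variables listed below". No list follows there. The only list comes in section 9 (Interaction with subgroups), which first says "A summary forest plot will be presented on the basis of the predefined subgroups" and then "The subgroup analysis included the following covariates: unbalanced baseline variables, age, sex, severity of depressive symptoms and pain severity after surgery".

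**Timing.** SAP section 3 (Planned analyses) says "The detailed procedure of analysis in this SAP will be performed only after the database is frozen" and "The intent-to-treat and per-protocol populations will be determined before unblinding the treatment allocation". It makes no such commitment for covariates or subgroups.

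**Status of these analyses.** The Main Model in SAP section 9 is an unadjusted chi-square or Fisher's exact test in the modified ITT population. The same section labels subgroup results exploratory, and the Protocol says the same of secondary outcomes and sensitivity analyses. The adjusted odds ratio for the main effect appears only in the Protocol. SAP section 9 uses the list only for the subgroup analysis.

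**The concern.** A variable can be called unbalanced only once the two arms have been set side by side. It therefore cannot belong to a predefined set, and on this point SAP section 9 contradicts itself. The documents do not say what counts as unbalanced (a p value, a standardised difference or judgement), which variables are candidates, or whether anyone would decide with treatment labels masked.

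In a properly randomised trial a baseline imbalance is a chance event and says nothing about whether the variable predicts remission. A model extended on that basis picks up variables by luck, and its final form is settled when data by arm can be seen. At stake are how far the supplementary adjusted odds ratio, which readers often take as confirming the primary result, was specified in advance, and the accuracy of the label on the forest plot.

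**Working it through.** The plan gives no figure for imbalance, so there is none to reproduce. The one planning figure used here is the 506 patients, or 253 per arm. It reproduces closely: 19.3% versus 10%, two-sided 0.05, 80% power, with continuity correction gives 247 per arm. Multiplying by 1.018 for one O'Brien-Fleming-type look at 75% gives 252 per arm, or 504 in total. Attrition: 253/0.9 = 281.1, rounded up to 282, and 2 × 282 = 564, as stated.

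**1. Candidates.** SAP Table 1 lists 30 variables (not counting the Other row). Age, sex, severe depressive symptoms and MADRS are already covered by the named list. 30 − 4 = 26.

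**2. Expected number flagged by chance.** This is 26 times the chance per variable. The documents name no rule, so three common ones are shown.

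| Rule (assumed) | Chance per variable | Expected of 26 |
|---|---|---|
| p<0.05 | 0.05 | 1.3 |
| p<0.10 | 0.10 | 2.6 |
| standardised difference >0.1 | 0.261 | 6.8 |

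For the third row, SE = √(2/253) = 0.0889, 0.1/0.0889 = 1.125, and 2 × [1 − Φ(1.125)] = 0.261. With 282 per arm the chance is 0.235 (26 × 0.235 = 6.1 flagged). With 212 per arm, the interim size, it is 0.303 (26 × 0.303 = 7.9 flagged).

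**3. Chance that at least one is flagged.** If the variables are independent, 1 − 0.95^26 = 0.74 at p<0.05. The expected counts in step 2 do not need independence; this figure does. Several variables overlap (the two WHODAS entries; PHQ-9 and HADS), and for approximately normal test statistics correlation can only lower the 74%.

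**4. Size of the model.** Expected remissions: 506 × (0.193 + 0.10)/2 = 74. Besides treatment, the model would carry 4 + 1.3 = 5.3 covariates on average under the first rule and 4 + 6.8 = 10.8 under the third, counting one term per variable.

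**5. Type I error of the adjusted test.** Two simulations with no treatment effect, both on illustrative assumptions:

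- 4,000 trials, 30 covariates of which 6 prognostic, linear regression with robust SE: 4.8–4.9% under each of the three rules, and 6.6% when the most favourable of the three is kept.
- 3,000 trials, 506 patients, 27 covariates of which 6 prognostic, logistic regression: 4.5% (p<0.05 rule), 4.4% (p<0.10 rule), 4.8% (fixed prognostic set), and 5.8% for the most favourable of three. The Monte Carlo SE is about 0.4 points. The standardised-difference rule alone was not reported in this run.

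Any one rule, fixed and followed, does no harm to the error rate. The modest excess comes from leaving the choice open.

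**The case against.** The strongest reply is that little depends on this. Nothing confirmatory uses the list. Age, sex, depressive severity and postoperative pain severity enter whatever the balance, so the model already holds the obvious prognostic factors, and the subgroup results are called exploratory. All of this stands, and it sets the limits of the point. It does not make the remaining subgroups predefined, and it does not supply the missing rule.

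A reader might infer more than the documents support:

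- *That imbalances decide the whole model or plot.* They only add to four named variables.
- *That the documents place the selection after unblinding.* They do not say whether labels would be open or masked. What can be said is that no masked step is described.
- *That the SAP plans significance tests of baseline characteristics.* Section 7 says "The modified ITT population will be tested for demographic characteristics and efficacy and safety outcomes", which can be read that way. But section 9 says demographics will be summarised, and the Table 1 shell, unlike Table 2, has no p-value column. This is loose wording and is not relied on here.
- *That the extra subgroups create a particular risk of false interactions.* That risk depends on how many subgroups are tested. The same number of fully prespecified subgroups would carry it too.

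**Conclusion.** The point holds for two supporting analyses: the Protocol's adjusted odds ratio and the SAP's exploratory forest plot. Each contains an open term that can be filled only by comparing the arms, with no rule to fill it, and the SAP's description of the subgroups as predefined is to that extent wrong. Depending on the rule adopted, the term adds on average about one to about seven variables to the four named. The candidate list (26) and the three rules are assumptions, since the documents give neither.

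It would be too strong to say that the trial's type I error is compromised. The primary test is unadjusted and untouched. For the adjusted test, no single rule inflated the error, and the 6–7% arises only if several rules are tried and the best is kept. The change is worth making because it costs almost nothing, but the primary conclusion does not depend on it.

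**What to change.** 1. Delete the unbalanced-variables term from the Protocol (Statistical analysis) and from SAP section 9 (Interaction with subgroups).
2. Before unblinding, fix the baseline covariates of the adjusted model on prognostic grounds: age, sex, and either baseline MADRS or the MADRS ≥30 randomisation stratum, plus any further Table 1 variables, each named at that time. Use the list whatever balance is observed.
3. Restrict the forest plot to a fixed list of baseline subgroups with stated cut-points, and place it where SAP section 8 refers to it.
4. Postoperative pain severity is named in advance, so it is not part of this point. It is, however, measured after treatment and may be affected by it, so it does not belong among baseline covariates or subgroups. If kept, it should be a separately labelled analysis.

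**Cost.** Wording in both documents. The 506/564 sample size and the primary test stay as they are. The downside is that an unexpected imbalance can then be adjusted for only in an analysis labelled post hoc. If the arms have already been compared, a list drawn up now must carry that label too.

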the anaesthesiologists in charge of the surgery. The anaesthesiologists, accessors, and patients will be blinded to the type of drug administered during surgery. The administered drug will be unmasked, with the agreement of the primary investigator, when esketamine-related severe adverse events occur (such as an allergy to the study drug) after the intervention and before the termination of surgery.

Outcomes

The primary outcome is the proportion of participants attaining remission (defined as a MADRS score less than or equal to 10) three days after surgery, based on an evaluation by blinded accessors at the bedside.

Secondary outcomes, including the differences in MADRS scores at three days and five days (or discharge) after surgery and the rates of patients achieving a response (MADRS scores reduced to or lower than half of the baseline MADRS score), the rate of severe pain within 72-hour postoperative period (severe pain is defined by the numeric rating scale pain scores equal to or more than 7).²¹

Safety outcomes include manic symptoms evaluated by the 11-item Young Mania Rating Scale (defined by YMRS scores more than or equal to 5) within the 3-day postoperative period,²² psychotic symptoms measured by a nonzero score on four particular items of the Brief Psychiatric Rating Scale (unusual thought content, suspiciousness, hallucinations, and conceptual disorganization) during the three days after surgery,^{23, 24} dissociative symptoms accessed by a nonzero score on the Clinician-Administered Dissociative States Scale within three days after the operation,²⁵ and all drug-related adverse events during surgery or before discharge.

Data management

The clinical data will be recorded and managed with the electronic database. The paper version materials including the protocol, the case reported forms, informed consent forms, and electronic version database will be preserved by the primary investigator and stored in the independently locked strongbox in Beijing Tiantan Hospital.

Sample size calculation

It has been reported that the remission rate difference in the antidepressant effects between esketamine and ketamine was 3.8% in treatment-resistant depression

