The null hypothesis of no difference in remission rate between the two arms of intervention will be analysed by a two-sided test at the 5% level of significance.

$$H_0: \lambda_1/\lambda_2 = 1$$

$$H_1: \lambda_1/\lambda_2 \neq 1$$

where λ_1 is the remission rate at postoperative day 3 in the group treated with esketamine and where λ_2 is the same timepoint in the group treated with placebo.

5. Sample size determination

The difference in the remission rates of antidepressant effects between esketamine and ketamine was reported to be 3.8% in patients with treatment-resistant depression. In the perioperative population with depressive symptoms, the remission rate was reported to be 23.1% in the ketamine group and 9.3% in the placebo group on the basis of the PASSION study at our research site. We assumed that the remission rate in the esketamine group would be 19.3% and that in the placebo group would be 10%.

A sample size of 506 participants provided 80% power to show the difference between the esketamine group and the placebo group (with a ratio of 1:1), including 1 interim analysis with a two-sided significance level of 0.05. Considering a 10% attrition rate, the total sample size is planned to be 564.

6. Interim analysis

The planned interim analysis will be performed after 424 patients (75% of the total sample size) have completed the follow-up. This interim analysis is based on the

intention-to-treat principle, and the p value is set at 0.019 following adjustment by the O'Brien-Fleming method. ^[6] The trial will be stopped after interim analysis if a significant difference between the groups is detected.

7. Population analysis

Total population

This population will comprise all the subjects screened and for whom a record exists in the study database. This population will be used for listing adverse events occurring prior to randomization and reasons for withdrawal occurring prior to randomization.

Modified Intent-to-Treat Population

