Patient-reported duration of illness		
< 1 month	n (%)	n (%)
1-3 months	n (%)	n (%)
Coexisting medical condition		
Diabetes	n (%)	n (%)
Hypertension	n (%)	n (%)
Stroke	n (%)	n (%)
Heart disease	n (%)	n (%)
Chronic pain	n (%)	n (%)
MDD	n (%)	n (%)
Motor dysfunction	n (%)	n (%)
Surgical history	n (%)	n (%)
ASA physical status	n (%)	n (%)
Charlson's comorbidity scores	Mean (SD)/median (IQR)	Mean (SD)/median (IQR)
Severe depressive symptoms	n (%)	n (%)
Recurrent malignancy	n (%)	n (%)
Preoperative assessment		
PHQ-9	Mean (SD)/median (IQR)	Mean (SD)/median (IQR)

MADRS	Mean (SD)/median (IQR)	Mean (SD)/median (IQR)
GAD-7	Mean (SD)/median (IQR)	Mean (SD)/median (IQR)
HADS	Mean (SD)/median (IQR)	Mean (SD)/median (IQR)
WHODAS 2.0 scores	Mean (SD)/median (IQR)	Mean (SD)/median (IQR)
Z-WHODAS 2.0	Mean (SD)/median (IQR)	Mean (SD)/median (IQR)
Type of surgery	n (%)	n (%)
Other ^a	n (%)	n (%)

Data are shown as the mean (SD)/median (interquartile range) and numbers (%).

Table 2. Primary outcome and Secondary outcomes.

Characteristics	Esketamine group	OR/Difference		P value
		Control group	(95%CI)	
Primary Outcome				
Remission on day 3	n (%)	n (%)	OR (95% CIs)	x
Secondary Outcomes				
NRS Pain scores >3, 0-48 Hours	n (%)	n (%)	OR (95% CIs)	x
Rescue analgesia, 0-48 Hours	n (%)	n (%)	OR (95% CIs)	x
Assessments on POD3				
MADRS	median (IQR)	median (IQR)	D (95% CIs)	x
GAD-7	median (IQR)	median (IQR)	D (95% CIs)	x
HADS	median (IQR)	median (IQR)	D (95% CIs)	x
PHQ-9≥10	n (%)	n (%)	OR (95% CIs)	x
Response	n (%)	n (%)	OR (95% CIs)	x
Assessments on discharge				
MADRS	median (IQR)	median (IQR)	D (95% CIs)	x
GAD-7	median (IQR)	median (IQR)	D (95% CIs)	x
HADS	median (IQR)	median (IQR)	D (95% CIs)	x
PHQ-9≥10	n (%)	n (%)	OR (95% CIs)	x
Response	n (%)	n (%)	OR (95% CIs)	x
Remission	n (%)	n (%)	OR (95% CIs)	x
Length of hospital stay	median (IQR)	median (IQR)	D (95% CIs)	x
Adverse events				
PONV, 0-48 Hours	n (%)	n (%)	OR (95% CIs)	x
Dissociative symptoms (CADSS≥5)	n (%)	n (%)	OR (95% CIs)	x
Psychotic side effects (BPRS 4 items≥5)	n (%)	n (%)	OR (95% CIs)	x
Manic symptoms (YMRS≥5)	n (%)	n (%)	OR (95% CIs)	x
Delirium	n (%)	n (%)	OR (95% CIs)	x
Infection after surgery	n (%)	n (%)	OR (95% CIs)	x
Bleeding events	n (%)	n (%)	OR (95% CIs)	x
Thrombus events	n (%)	n (%)	OR (95% CIs)	x

Figure 1 Flow chart and consort diagram of the study

Figure 2 Primary outcomes and MADRS scores

Figure 3 Subgroup analysis and interactions

10. Reference

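### The SAP departs from the Protocol's definitions of dissociation and severe pain, and names two incompatible safety sets

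*SAP*

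**What the plan says.** **Dissociation.** The Protocol (Outcomes) lists as a safety outcome "dissociative symptoms accessed by a nonzero score on the Clinician-Administered Dissociative States Scale within three days after the operation". The Table 2 row in SAP section 9 reads "Dissociative symptoms (CADSS≥5". SAP section 2 names dissociative symptoms over the first three days but gives no cut-off, so Table 2 holds the SAP's only definition.

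**Safety set.** SAP section 7 says the modified ITT population serves the primary analysis of both efficacy and safety. That population leaves out, among others, patients whose surgical complications (aphasia and coma are the examples) prevent follow-up. SAP section 9, Safety analysis, says instead: "Safety endpoints will be assessed in the total population". Section 7 defines the total population thus: "This population will comprise all the subjects screened and for whom a record exists in the study database". It gives the use as follows: "This population will be used for listing adverse events occurring prior to randomization", together with reasons for withdrawal before randomisation. Section 9 nevertheless wants the safety variables "presented as frequency counts and percentages in both the esketamine group and the control group".

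**Pain.** The Protocol's secondary outcome is severe pain, NRS 7 or more, within 72 hours. SAP section 2 has moderate-to-severe pain over three days and attaches a cut-off of more than 3 to severe pain. The Table 2 row is NRS above 3 over 0 to 48 hours.

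**Psychotic symptoms.** The Protocol asks for a nonzero score on four named BPRS items. Table 2 asks for 5 or more on the four items.

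**The concern.** Two outcomes that the Protocol defines, dissociation and severe pain, would be reported under other rules or not at all. The SAP claims accordance with the published protocol, and its version history gives no reason for a change. Dissociation matters here because the Protocol's own Discussion names it as a risk that esketamine may increase.

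The safety set is a separate problem. Of the two sets named, one as defined includes people who were never randomised and so belong to no arm. The other removes some treated patients because of what happened to them after dosing. Surgery-related complications are themselves a listed safety endpoint in SAP section 2, so some cases of that endpoint would leave the analysis, along with any other adverse events those patients had. The analyst is left to choose.

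**Working it through.** The documents give no CADSS distribution, pain distribution or exclusion count, so there is no figure of the plan's to reproduce. The check compares the texts and then shows by illustration what could change. All event counts below are assumptions. The arm size is 564/2 = 282. Intervals are Wald intervals on the log odds ratio, with SE = √(1/a + 1/b + 1/c + 1/d), where a and c are the events and b and d the non-events in the two arms.

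**1. CADSS cut-off.** Every patient with a score of 5 or more also has a nonzero score, so the SAP count is equal to or below the Protocol count. Each patient scoring above 0 but below 5 lowers that arm's rate by 1/282 = 0.35 percentage points. The contrast between arms can move either way:

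| Assumed case | Rule | Esketamine vs placebo | OR (95% CI) |
|---|---|---|---|
| (a) half of scorers in each arm are below 5 | nonzero | 28 vs 14 | 2.11 (1.09 to 4.10) |
| | 5 or more | 14 vs 7 | 2.05 (0.82 to 5.16) |
| (b) 56 patients per arm score below 5 | nonzero | 84 vs 70 | 1.28 (0.89 to 1.86) |
| | 5 or more | 28 vs 14 | 2.11 (1.09 to 4.10) |

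First row worked: OR = (28 × 268)/(14 × 254) = 2.11; SE = √(1/28 + 1/254 + 1/14 + 1/268) = 0.339; exp(0.747 ± 1.96 × 0.339) = 1.09 to 4.10.

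**2. Safety set.** The two statements cannot both hold. The Table 1 title, "Table 1. Demographic and preoperative characteristics of the total population", also heads a by-arm table, so section 9 may intend randomised patients. Section 7's definition says otherwise.

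For the modified ITT set, let one arm have x events among 282 treated patients, with k excluded, c of whom had the event. The reported rate is (x − c)/(282 − k). With x = 28, the treated-set rate is 28/282 = 9.93%.

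| k | c = k (all excluded had the event) | c = 0 (none had it) |
|---|---|---|
| 5 | 23/277 = 8.30% | 28/277 = 10.11% |
| 3 | 25/279 = 8.96% | 28/279 = 10.04% |

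With five excluded, the shift in a single Table 2 row runs from −1.63 to +0.18 points.

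**3. Pain.** Scores of 4 to 6 count in the SAP but not in the Protocol. Section 2 keeps the 72-hour window, so its count is at least as large as the Protocol's. Table 2 covers only 48 of the 72 hours, so it can also miss severe pain that first occurs after 48 hours. The net direction for Table 2 is not determined. A cut-off of 7 appears nowhere in the SAP.

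**4. BPRS.** If items are scored from 1, the floor for four items is 4, and a total of 5 or more means any symptom above the floor. If items are scored from 0, 5 or more is stricter than nonzero. The documents do not give the scoring, so whether the two rules differ in practice is open.

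**5. What agrees.** The YMRS cut-off (5 or more) and the three-day psychiatric window are the same in both documents.

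**The case against.** The SAP says it is to be used together with the Protocol, so an outcome it omits is not thereby cancelled. Table 2 is also plainly not exhaustive, since it has no rows for the 1-, 3- and 6-month outcomes in section 2. That weakens any argument from absence in Table 2 alone. It does not help where the SAP states a different rule: Table 2 gives an explicit CADSS cut-off, and section 2 attaches an explicit and different cut-off to severe pain. The words severe pain and a three-day window do appear in section 2. What is missing is the outcome as the Protocol defines it.

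The SAP postdates the Protocol and refers to amendments, so the changes may be deliberate. That cannot be excluded, but nothing in these documents reconciles the definitions. Calling secondary outcomes exploratory limits the inference drawn from them; it does not change what they are.

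The illustrative counts are chosen, and they show what is possible, not what is likely. That stands. It also stands that patients in coma or with aphasia may be unratable on CADSS, BPRS or YMRS in any set, so the larger shift in the modified ITT example applies mainly to rows such as bleeding, infection or thrombus. Finally, the missing-data text in SAP section 8 replaces missing assessments with negative results. If that rule reached the safety scales, unassessable patients kept in the set would count as event-free, so the choice of denominator matters.

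**Conclusion.** The point holds. As written, the SAP would report a dissociation rate that is not the Protocol's safety outcome, would not report severe pain as the Protocol defines it, and gives two safety sets that cannot both be used. For dissociation, the direction within each arm is certain (equal or lower), but the effect on the comparison is not. For the modified ITT set, a shift of −1.63 to +0.18 points in one row rests on assumed figures of 28 events and five exclusions in an arm of 282. Actual sizes cannot be derived from the documents. The BPRS difference is a matter for clarification only. The primary endpoint definition is untouched, so this should be corrected but does not threaten the main efficacy question.

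**What to change.** - **CADSS:** in Table 2, report a nonzero score within three days as the Protocol-defined outcome, and keep 5 or more as a labelled additional row.
- **Pain:** add NRS 7 or more within 72 hours to section 2 and Table 2. Keep above 3 as a labelled additional outcome, with the same window in both places.
- **Safety set:** name one set in sections 7 and 9. Section 7 already describes a suitable one: "The intent-to-treat (ITT) population will include all the subjects after randomization and who received esketamine or placebo during surgery". Report it by arm, with no exclusion for postoperative complications. For each rating scale, show the number assessable and use it as the denominator.
- **BPRS:** state the item scoring and reconcile the two definitions.

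The cost is SAP wording and a few table rows, using assessments that the Protocol's outcomes already require. The dissociation rate may rise and cannot fall when counted by the Protocol's rule. Moving from the modified ITT set to the treated set can shift other rates either way.
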